6.1 Study drug

6.1.1 Source of drug

Investigational medicinal product: Tongxinluo Capsules

Ingredients: Ginseng Radix, Hirudo nipponia whitman, Buthus martensi karsch, Eupolyphaga

Steleophaga, Scolopendra, Cicadae Periostracum, Paeoniae Radix Rubra, Borneolum

Syntheticum, Santali Albi Lignum, Dalbergiae Odoriferae Lignum, Frankincense and Ziziphi

Spirosae Semen.

Description: This product is a hard capsule, with content consisting of gray-brown to grayish-

brown granules and powder. It has a fragrant odor, a slight fishy smell, and a mildly salty and

bitter taste.

Strength: 0.26 g/capsule

Batch No.: GYZZ Z 19980015

Manufacturer: Shijiazhuang Yiling Pharmaceutical Co., Ltd.

Investigational medicinal product: Placebo

Tongxinluo Capsule Simulant (The simulant is identical to Tongxinluo Capsules in terms of

color, strength, packaging, labeling, and description of the content).

All the investigational medicinal products mentioned above are provided free of charge by

Shijiazhuang Yiling Pharmaceutical Co., Ltd., and come with COAs.

6.1.2 Formulation, packaging, and labeling

[figure not shown]
Tongxinluo Capsules will be provided in the form of 0.26 g capsule formulation, and the

placebo will have an appearance identical to it.

[figure not shown]
Drug packaging

Small packaging: The appearance is as follows, with the words "For Clinical Study Use" printed

on it. Each small box contains 30 capsules packed in aluminum-plastic sheets.

Large packaging: It is a white cardboard box measuring 29.5 cm × 12 cm × 22 cm. Each large packaging contains 38 small packages, and each large box is labeled as follows:

Thank you for your trust and support! Please be sure to follow the doctor's advice and attend the hospital for treatment on the specified dates. Thank you for your cooperation!

6.1.3 Storage method

The investigational medicinal product should be securely stored with a lock in a controlled indoor area, with attention to preventing moisture. Each center must designate a person in charge of storage and management of investigational medicinal products.

6.1.4 Dispensing and retrieval of drug

Every time the investigator dispenses drug to the subject during a follow-up visit, it is necessary to complete the Drug Dispensing Register, accurately and promptly record the quantity of dispensed drug, and remind the subject to bring back the remaining drug during the next visit. Additionally, when retrieving drug, verify the returned quantity and document it in the Drug Dispensing/Return Register. At the end of the study, all remaining drug should be returned to

the sponsor. The Drug Retrieval Form should be completed, and any unused drug must be sealed when returned. After the study concludes, the remaining drug will be retrieved by the sponsor's CRA and disposed of uniformly.

6.1.5 Drug inventory

After self-administration of the drug, the subject should return all remaining drug during each visit. The investigator will count the remaining drug and record the quantity, which is used to assess compliance.

6.1.6 Handling plan for temporary discontinuation, permanent discontinuation, or loss to follow-up of patients

The study drugs should be continued for as long as possible. If discontinuing the study drug, temporary discontinuation should be considered in case of loss to follow-up, and permanent discontinuation is the last resort. Any discontinuation of drug should be thoroughly documented on the corresponding pages of the CRF. In any circumstance, patients should participate in the study for as long as feasibly possible. Under any circumstance, pregnancy will result in permanent discontinuation from the study.

6.1.6.1 Temporary suspension of study drug

Once the investigator, based on their best clinical judgment, deems it unlikely that the study drug is related to the events that occurred, and in the absence of other study contraindications, the drug should be resumed. Resumption of drug should be carried out under close and rational monitoring. If it is determined that the trial can be resumed, the investigator should document the time of resumption for all temporary discontinuations (less than 10 days) on the corresponding pages of the CRF.

6.1.6.2 Definite indications for discontinuing study drug

Patients should discontinue the study drug in the following circumstances:

Clinical conditions necessitating discontinuation of the drug (e.g., abnormal laboratory values)

Pregnancy or a desire to become pregnant

6.1.6.3 Handling plan for patients permanently discontinuing the drug

The follow-up of patients should adhere to the procedures specified in the study protocol, continuing until the scheduled completion date of the study or until the patient recovers to normal or stable condition from adverse events (whichever is longer).

The investigator should record all confirmed withdrawals from the study on the corresponding pages of the CRF.

Patients who discontinue the study drug before the last follow-up should complete the endpoint follow-up at 3 months.

For patients lost to follow-up, relevant information should be documented up to the last follow-up in their CRFs. The investigator should make every effort to contact each patient, ascertain the reason for loss to follow-up, and assess their health status.

6.1.6.4 Outcomes

Patients who have withdrawn from the study cannot re-enter the study. The patient's random number and treatment drug will no longer be applicable.

The investigator should communicate with the sponsor to jointly confirm the interruption and/or withdrawal of the patient.

Randomized patients will not be replaced.

6.2 Treatment regimen

6.2.1 Study process:

Screening period (Day -3 to Day 0):

If patients meet the treatment criteria outlined in this protocol, they can undergo all examinations during this period. Patients who meet the inclusion criteria will proceed to the randomization phase.

Random treatment period (Day 1 to Day 90): Designated as Day 1 from the first dose administration.

Treatment group: Standard treatment + Tongxinluo Capsules (4 capsules/time, tid, po)

Control group: Standard treatment + Tongxinluo Capsule Simulant (4 capsules/time, tid, po)

It is recommended to take the study drugs in approximately 30 minutes after daily meals. Patients should not take the drug in the morning of the day of visit at home. If a patient misses a dose on a certain day, the dose the following day should not exceed the daily dose. Dose adjustment of the study drug is not allowed. If a patient develops an intolerable adverse event, which is considered by the investigator to be related to the study drug, he/she should terminate the treatment with the study drug.

6.2.2 Standard treatment

Refer to the *Guidelines for diagnosis and treatment of acute ischemic stroke in China 2010* for the recommended Standard treatment plan (see Appendix 7).

6.2.3 Concomitant medications

During the study, the use of concomitant medications as needed is as follows: General supportive treatment includes antipyretics, diuretics, antihypertensive drugs, lipid-lowering agents, hypoglycemic agents, antibiotics, and other symptomatic medications. However, during the study, it is advisable to avoid the use of traditional Chinese medicines or proprietary Chinese medicines that may affect the assessment of therapeutic efficacy.

From the onset of the illness until the end (discontinuation) of the study, the use of other investigational drugs is prohibited.

All concurrently used medications and other treatment modalities should be thoroughly documented in the study medical records, along with appropriate explanations.

6.2.4 Course of treatment: 90 days.

6.3 Compliance assessment

Compliance assessment of subjects will be conducted by thoroughly documenting the dispensing and retrieval of drugs. Actual drug intake within the range of 80% to 120% of the prescribed dosage will be considered as compliant with the protocol requirements.

6.4 Adverse drug reactions

Individual patients may experience mild stomach discomfort after taking the drug.

7 Clinical observation endpoints and indicators

7.1 Clinical observation endpoints

7.1.1 Primary efficacy endpoint

Improvement in self-care ability (proportion of patients with mRS score ≤1) after 90 days of treatment

7.1.2 Secondary efficacy endpoint

1. Improvement in neurological deficit (proportion of patients with NIHSS ≤1 or NIHSS improved by 4 points or more)

- 2. Improvement in activities of daily living (proportion of patients with BI index \geq 85)
- 3. Disability rate (proportion of patients with mRS score \geq 3 points);
- 4. Continuous changes of mRS scores;
- 5. Incidence of ischemic cerebrovascular disease during follow-up;
- 6. Incidence of combined vascular events during follow-up;

7.2 Safety indicators:

- Adverse event assessment
- Clinical laboratory indicators include blood routine (hemoglobin, red blood cells, white blood cells, platelets), urine routine (urine protein, urine white blood cells, urine red blood cells), serum biochemistry (alanine aminotransferase, aspartate aminotransferase, alkaline phosphatase, glutamine, urea nitrogen, creatinine, total bilirubin, blood glucose, total cholesterol, triglycerides, low-density lipoprotein, high-density lipoprotein).
- Coagulogram: Coagulation 4-item (PT, APTT, TT, FIB)
- 12-lead ECG
- Physical examination

8 Study Process

Refer to Table 1 for details of the study process.

8.1 Visit 1 (V1, Day -3 to Day 0)

(Complete the following tasks within 3 days)

- Sign the *Informed Consent Form*
- Collect general information: gender, age, height, weight, etc.
- Perform brain CT and/or head MRI examination
- Laboratory tests (If the patient has undergone tests during the current hospitalization
 that overlap with the study examination items, there is no need to repeat the tests.
 Instead, the report of these tests should be reprinted or copied and attached to the study
 medical record. The copy must be signed by the investigator.)
- Physical examination
 - 12-lead ECG
 - Pregnancy test

- Assess NIHSS score, mRS score, and BI index score
 - Record concomitant diseases and concomitant medications
- Review inclusion criteria and exclusion criteria
 - Dispense randomized study drugs
- Advise the subjects of the next follow-up date and inform them not to take the drug on the day of the follow-up

Since neuroimaging is routinely recommended for all stroke patients, this study will not cover the cost of this portion during this visit.

8.2 Visit 2 (V2, 7d)

- Record adverse events
- Record concomitant medications
- Physical examination
- Perform scale assessment (NIHSS, mRS, BI Index)
- Record combined vascular events
- Advise the subjects of the next follow-up date and inform them not to take the drug on the day of the follow-up

8.3 Visit 3 (V3, at discharge)

- Record adverse events
- Record concomitant medications
- Physical examination
- Perform brain CT and/or head MRI examination (If this examination is conducted at discharge, the results should be recorded in the CRF. If the patient did not undergo imaging examination at discharge, record it as "None" in the CRF)
- Laboratory test
 - Measure 12-lead ECG (Both of the above are routine examinations at discharge for patients. This study will not cover the cost of these examinations during this visit, but the results of these two examinations need to be collected for safety observation.)
 - Perform scale assessment (NIHSS, mRS, BI Index)

- Record combined vascular events
- Advise the subjects of the next follow-up date and inform them not to take the drug on the day of the follow-up

8.4 Visit 4 (V4, 90 d)

- Laboratory test
- Physical examination
- Record adverse events
 - 12-lead ECG
 - Head MRI examination: Centers participating in the radiology subgroup should complete the TI + T2 + DWI + FIAIR + MRA + T2* examination.
 All images should be saved in DICOM format, and the DICOM CD will be transferred to the Central Imaging Evaluation Laboratory. (Refer to Appendix 6–Summary of the Radiology Subgroup Study for details)
 - Perform scale assessment (NIHSS, mRS, BI Index)
 - Record combined vascular events
 - Retrieve the remaining drug and assess medication compliance
 - Record the completion status of the study

8.5 Visit 5 (follow-up visit if necessary) *

*Due to the persistent adverse events or clinically significant laboratory abnormalities or vital sign abnormalities that exist at the end of treatment, the investigator considers it necessary to conduct a follow-up visit to obtain follow-up measurement results. The investigator will conduct follow-up visits based on the specific situation, which may also be done via telephone.

8.6 Follow-up for potential events

If a patient experiences potential clinical neurological events, including clinical symptoms due to ischemia or new transient or persistent neurological symptoms, each center is required to generate a determination document within 72 hours. The content should include:

- Conduct neurological examination (mRS, NIHSS, BI)
- Perform physical examination, record body weights and vital signs
- Collect information on concomitant medications and adverse events since the last Page 18 of 76

follow-up.

 Patients participating in the radiology subgroup should undergo MRI sequence examinations, and their imaging results should be transmitted to the central imaging reading room.

If a patient experiences a new potential cardiovascular event, a cardiac assessment, including an ECG, will be conducted based on clinical need. Any information supporting a potential myocardial infarction will be collected in the determination document and communicated to the CRA within 72 hours.

9 Efficacy and Safety Determination Criteria

9.1 Efficacy determination criteria

9.1.1 Primary efficacy assessment

• The proportion of patients with improvement in activities of daily living 90 days after treatment (mRS score ≤1): mRS ≤1 indicates complete or substantial recovery of activities of daily living, representing a favorable prognosis. Comparison of the proportion of patients with favorable prognosis in the treatment group and the control group 90 days after randomization;

9.1.2 Secondary efficacy assessment:

- Improvement in neurological deficit, i.e., the proportion of patients with NIHSS ≤1 or NIHSS improved by 4 points or more: NIHSS score ≤1 or reduction of ≥4 points is considered effective; compare the proportion of effective and ineffective patients and continuous changes of NIHSS in the treatment group and the control group after 90 days of randomized treatment;
- Proportion of patients with BI index ≥85: BI score ≥85 indicates the ability to live
 independently. Compare the proportion of patients able to live independently between
 the treatment group and the control group 90 days of randomized treatment, as well as
 continuous changes in BI scores between the two groups;
- Disability rate, defined as the proportion of patients with an mRS score ≥3: An mRS score ≥3 indicates the inability to live independently. Compare the percentage of disabled patients between the treatment group and the control group 90 days of

randomized treatment:

- Continuous changes in mRS scores: Compare the changes in mRS scores between the treatment group and the control group at different visit points, including baseline, 7 d, discharge, and 90 d;
- Incidence of ischemic cerebrovascular events during the follow-up period: The
 proportion of ischemic stroke or TIA within 90 days of randomized treatment, or
 newly occurring ischemic lesions detected on MRI at the last visit, will be assessed as
 a group or separately;
- Incidence of combined vascular events during the follow-up period: The cumulative
 incidence of newly occurring combined vascular events within 90 days of randomized
 treatment will be assessed as a group or separately;

Definition of combined vascular events: Consist of any type of stroke (ischemic stroke, hemorrhagic stroke), TIA, myocardial infarction, and vascular death.

Vascular death: Hemorrhagic death of any organ or fatal pulmonary embolism.

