9.1.2.1 Assessment and Procedures for Combined Vascular Events

After the occurrence of a combined vascular event, the study center must notify the sponsor within 24 hours upon receipt of the event notice. Vascular events will be reviewed by an independent Clinical Events Committee (CEC). Therefore, the endpoint event classification table will be included as part of the CRF. The investigator will record events in the aforementioned table and promptly submit supporting documents (admission and discharge records, medical records, death records, ECG, etc.). This information will be provided to the CEC for the determination of events.

The CEC is composed of a chairperson and 5–6 members. Each event will be independently reviewed by two members of the committee, and the conclusions will be submitted to the chairperson of the committee. If there is a disagreement between the two reviewing members or between the two reviewing members and the chairperson, when the number of dissenting events reaches a certain threshold, the entire committee will schedule a meeting to review the events.

9.2 Safety determination:

Adverse event assessment

• Clinical laboratory indicators:

Collect blood and urine samples in a fasting state (at least 10 hours of fasting, with water intake allowed but no consumption of coffee or tea) and send them to the laboratories of each center for testing according to uniform standards

Blood routine (hemoglobin, red blood cells, white blood cells, platelets), urine routine (urine protein, urine white blood cells, urine red blood cells), serum biochemistry (alanine aminotransferase, aspartate aminotransferase, alkaline phosphatase, total bilirubin, glutamine, urea nitrogen, creatinine, uric acid, blood glucose, total cholesterol, triglycerides, low-density lipoprotein, high-density lipoprotein), coagulation 4-item

12-lead ECG

Physical examination:

Comprehensive physical examination: General condition (including height, weight), vital signs (including blood pressure, pulse rate), skin (including hair and nails), eyes, ears, nose, and throat, neck/thyroid, chest/lungs, cardiovascular system, abdomen/gastrointestinal system, reproductive-urinary system (optional), nervous system, lymphatic system, and musculoskeletal system;

Simplified physical examination: General condition (including weight), vital signs (including blood pressure, pulse rate), chest/lungs, cardiovascular system

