2. TIA

3. Myocardial infarction

The following events are considered both endpoint events and AE/SAE

1. Hemorrhagic stroke

2. Vascular death

All deaths and any hemorrhagic events should be reported as AE/SAE

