5.2 Secondary effect index

1. Improvement of neurological deficits (ratio of NIHSS≤1 or improve 4 score or more);

Improvement of neurological deficits (ratio of NIHSS≤1 or improve 4 score or more): It is effective for NIHSS≤1 or reducing 4 points or more; compare the ratio of efficacy and inefficacy and the continuous change of NIHSS between treatment group and control group 90 days after random treatment;

2. Improvement of daily life ability (ratio of BI index ≥85);

Ratio of patients with BI index≥85: BI score≥85 indicates the patient with ability of independent living; compare the ratio of patient with ability of independent living and continuous change of BI between treatment group and control group at 90 days after random treatment;

3. Disability rate (ratio of mRS score \geq 3)

mRS≥3 indicates the patient without self-care ability; compare the disability rate between treatment group and control group at 90 days after random treatment;

4. Continuous change of mRS score

Compare change of mRS score at baseline, 7d, discharge day and 90d between treatment group and control group;

5. Incidence of ischemic cerebrovascular diseases during follow-up period;

Ratio of ischemic stroke or TIA within 90 days after random treatment, or ratio of new ischemic focus detected by MRI during the last visit, and take this kind of patients as a group for evaluation or respective evaluation:

6. Incidence of combined vascular events during follow-up period;

Accumulated ratio of patients having newly combined vascular events within 90 days after random treatment;

Definition of combined vascular events: Include any type of stroke (ischemic stroke and hemorrhagic stroke), TIA, myocardial infarction and vascular death.

Vascular death: Hemorrhagic death or fatal pulmonary embolism of any organ.

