Note: Ischemic cerebrovascular diseases during follow-up period include: Ischemic stroke or TIA within 90 days after random treatment, or new ischemic focus detected by MRI at the last visit

7.3.8 Secondary effect index – incidence of combined vascular events during follow-up period Table 7.3.8.1 Inter-group comparison of incidence of ischemic stroke within 90 days after treatment The same as Table 7.3.7.1

Table 7.3.8.2 Inter-group comparison of incidence of myocardial infarction within 90 days after treatment. The same as above

Table 7.3.8.3 Inter-group comparison of incidence of vascular death within 90 days after treatment The same as above

Table 7.3.8.4 Inter-group comparison of incidence of vascular death during follow-up period

		FAS		PPS	
		Treatment		Treatment	
Item	Index	group	Control group	group	Control group
	With n(%)				
Combined vascular events	Without n(%)				
during follow-up period					
	N (Missing)				
	Statistics				
	P value				

Note: Definition of combined vascular events: Include any type of stroke (ischemic stroke and hemorrhagic stroke), TIA, myocardial infarction and vascular death.

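### Vascular death is defined only as haemorrhagic death or fatal pulmonary embolism, so the vascular-death table omits ischaemic and cardiac deaths and the composite misses some of them

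*Combined protocol and SAP*

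**What the plan says.** Protocol 9.1.2 builds the composite from five components: "Definition of combined vascular events: Consist of any type of stroke (ischemic stroke, hemorrhagic stroke), TIA, myocardial infarction, and vascular death". It counts new events only, as the cumulative "incidence of newly occurring combined vascular events within 90 days of randomized" treatment. The line that follows the composite defines its last component: "Vascular death: Hemorrhagic death of any organ or fatal pulmonary embolism".

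SAP 5.2 repeats this with a different word order: "Vascular death: Hemorrhagic death or fatal pulmonary embolism of any organ". The two documents agree in substance, since both name two causes of death and no others.

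Vascular death is used in two ways. It is a component of the composite, and it has its own comparison, "Table 7.3.8.3 Inter-group comparison of incidence of vascular death within 90 days after treatment".

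Protocol 9.1.2.1 sends combined vascular events to an independent CEC, with supporting papers that include death records. It gives no further rule for classifying a death. On safety, Protocol 10.4.2 adds: "All deaths and any hemorrhagic events should be reported as AE/SAE".

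**The concern.** In a trial of acute ischaemic stroke one expects vascular death to cover death from the stroke itself, from a recurrence, and from cardiac disease. Here it covers only bleeding deaths and pulmonary embolism. A reader of Table 7.3.8.3 would take it for a comparison of vascular mortality, when deaths from ischaemic stroke and from the heart are outside it. In the composite, a patient who dies of the index infarct, or suddenly of cardiac causes with no confirmed MI, would be recorded as having had no event or as missing, because Table 7.3.8.4 offers only with, without and missing.

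Index-stroke death is a realistic case. Patients enter within 72 hours of onset with NIHSS up to 22 (Protocol 5.1), and the treatment guideline in Appendix 7 names brain oedema and raised intracranial pressure after severe ischaemic stroke among the main reasons for death.

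**Working it through.** **1. Is the definition widened anywhere?** The synopsis lists vascular death as a component without defining it. Protocol 9.1.2.1 describes how the CEC works but not what counts as a vascular death. Protocol 10.4.2 lists vascular death as both an endpoint event and an AE/SAE, again without a definition. SAP 7.3.8 repeats the components in a footnote. The two-cause definition in Protocol 9.1.2 and SAP 5.2 is therefore the only one available.

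**2. What happens to each type of death under the text as written?** Nothing in the composite restricts stroke or MI to non-fatal events.

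| Cause of death within 90 days | Vascular death (Table 7.3.8.3) | Composite (Table 7.3.8.4) |
|---|---|---|
| Haemorrhagic stroke | counted | counted |
| Other fatal haemorrhage | counted | counted |
| Pulmonary embolism | counted | counted |
| New ischaemic stroke | not counted | counted, as ischaemic stroke |
| Recognised MI | not counted | counted, as MI |
| Index ischaemic stroke, no new event and no fatal bleed | not counted | **not counted** |
| Sudden cardiac death, MI not confirmed | not counted | **not counted** |
| Heart failure or other cardiac death | not counted | **not counted** |

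Five of the eight rows are missing from the stand-alone table, and three of those five are also missing from the composite.

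**3. Does another planned table recover these deaths?** All deaths are reported as AE/SAE, so the data exist. However, the SAP's adverse-event comparison (Table 7.4.1.1) has no row for death, and the mRS in Appendix 2 runs from 0 to 5 with no level for death. No other planned between-group table shows deaths as such.

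**4. Component tables.** SAP 7.3.8 runs from .1 to .4: ischaemic stroke, MI, vascular death, composite. TIA is in Table 7.3.7.2. Haemorrhagic stroke, a named component, has no table. Table 7.3.8.4 is titled "Inter-group comparison of incidence of vascular death during follow-up period", although its row and its footnote concern the composite.

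**5. Can the loss be sized?** No. The documents give no rate for vascular death, cardiac death or the composite. Protocol section 3 cites stroke mortality of 10% to 15% in general, with no time frame, which cannot be applied to this selected population.

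**6. Is the sample size affected?** No. It rests on mRS ≤1 at 90 days, 40% versus 47%, two-sided alpha 0.05, power 80%. With a pooled proportion of 0.435:

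n = [1.960 × √(2 × 0.435 × 0.565) + 0.842 × √(0.40 × 0.60 + 0.47 × 0.53)]² / 0.07² ≈ 786.2, rounded up to 787 per arm, as stated.

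787 / 0.8 = 983.75, rounded up to 984 per arm and 1,968 in total, also as stated. None of these inputs involves vascular death.

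**The case against.** **The composite keeps many of these deaths.** A reader might infer that it cannot show any effect on fatal ischaemic outcomes. The documents do not support that. A new fatal ischaemic stroke or a recognised fatal MI enters through its own component, and since the outcome is with or without per patient, relabelling those deaths would not change the composite. This objection stands and limits the point to the last three rows of the table above, plus the stand-alone comparison.

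**The size is unknown.** One could assume 90-day mortality of 1% to 5% and an ischaemic or cardiac share of 50% to 70%: 1,968 × 0.01 × 0.50 ≈ 10 to 1,968 × 0.05 × 0.70 ≈ 69 deaths. Neither input is in the documents. The result would also count deaths left out of the label, including some that the composite still captures. The exclusions for impaired consciousness, severe limb weakness, inability to swallow capsules and short life expectancy (Protocol 5.2) would tend to lower mortality. It should not be read as an estimate of events lost.

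**No bias is shown.** The same definition applies to both blinded arms. That is fair: the documents establish lost events, not a direction of error. Nor do they show that the CEC would be bound to call these deaths non-vascular, since neither a charter nor the classification table is reproduced.

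**The wording may be a translation fault.** The SAP version attaches any organ to pulmonary embolism, which makes no sense. This is possible and cannot be settled here, but the narrow list appears in both documents, so both need correcting in either case.

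**Crude proportions.** A reader might infer from the protocol's reference to cumulative incidence, together with the 20% drop-out allowance, that a time-to-event analysis is required. The documents do not support this. SAP 5.2 describes an accumulated proportion of patients within 90 days, both documents analyse secondary outcomes by the primary method, and Protocol 6.1.6.3 requires the 3-month endpoint follow-up after the study drug is stopped. A fixed-window proportion is a legitimate choice.

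**Conclusion.** The point holds as a gap in an endpoint definition, not as a contradiction between protocol and SAP. Applied literally, the definition removes all ischaemic-stroke and cardiac deaths from Table 7.3.8.3. From the composite it removes deaths from the index stroke without a new event, sudden cardiac deaths without confirmed MI, and other cardiac deaths. The number affected cannot be derived from the documents.

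The conclusion assumes that the CEC would apply the written definition and that stroke and MI include fatal events, as nothing says otherwise. A secondary endpoint is affected; the primary endpoint and sample size are not. It should be corrected because the wording is plain, the stand-alone table would mislead, and the correction is cheap. The title of Table 7.3.8.4 and the missing haemorrhagic stroke table are minor faults in the table shells.

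**What to change.** In Protocol 9.1.2, SAP 5.2 and the CEC classification form, define vascular death by one explicit list: death from ischaemic stroke (index or recurrent), haemorrhagic stroke, MI, sudden cardiac death, heart failure, pulmonary embolism, other haemorrhage, and other vascular cause. State that the CEC assigns the cause under blinding. Because submission to the CEC is currently triggered by a combined vascular event, also say that every reported death is sent for classification; otherwise an index-stroke or sudden cardiac death might never reach the committee.

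In SAP 7.3.8, retitle Table 7.3.8.4 as combined vascular events and add a component table for haemorrhagic stroke. The method of analysis need not change.

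The cost is an edit to the endpoint wording, the CEC form and two table shells, plus CEC review of deaths not now submitted. All deaths are already reported as AE/SAE, and death records are already among the papers supplied to the CEC for vascular events, so little or no new data collection should be needed.
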